9.3. Vital Signs, Physical Findings, and Other Observations Related to Safety

9.3.1. Vital Signs

Descriptive statistics for vital signs will be presented by treatment group for systolic blood pressure, diastolic blood pressure, heart rate, and body weight at each visit starting at baseline. Change from baseline to post-baseline visit will be presented. No formal statistical comparisons will be performed. Data will be attributed to visits as described in Section 6.2.6.

The incidence rates of PDLC for vital sign by parameter will be summarized (altogether, not by visit).

The incidence rates will be presented by treatment group. There will be no formal statistical testing.

A listing will present all values for a subject and vital sign parameter if at least 1 post-baseline value for that subject and parameter meets the PDLC criterion.

Table 10 presents criteria for categorizing the change from baseline in vital signs as PDLC.

Table 10: Pre-defined Limits of Change Criteria for Vital Signs

Vital Sign	Criteria
Pulse rate	≥ 120 bpm at any time post-dose and ≥ 15 bpm increase from baseline at any time post-dose
	≤ 50 bpm at any time post-dose and ≥ 15 bpm decrease from baseline at any time post-dose
Systolic blood pressure	≥ 180 mm Hg at any time post-dose and ≥ 20 mm Hg increase from baseline at any time post-dose
	≤ 90 mm Hg at any time post-dose and ≥ 20 mm Hg decrease from baseline at any time post-dose
Diastolic blood pressure	≥ 105 mm Hg at any time post-dose and ≥ 15 mm Hg increase from baseline at any time post-dose
	≤ 50 mm Hg at any time post-dose and ≥ 15 mm Hg decrease from baseline at any time post-dose
Weight	Change: > 5% increase from BL
	Change: > 5% decrease from BL

Abbreviations: bpm = beats per minute; mm Hg = millimeters mercury; PDLC = pre-defined limit of change

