12.3.7. Vital Signs

Vital signs include blood pressure (systolic and diastolic), respiration rate, heart rate, and temperature. Blood pressure measurements should be obtained using the same arm.

Measurements will be taken with the subject in sitting position after having rested for a 5-minute period. The same position should be used at all visits.

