15.3.2.5. Safety Analyses

Safety analyses will be based the safety population. Safety data will be summarized using counts and percentages for categorical data and descriptive statistics (mean, standard deviation, median, minimum, maximum) for continuous data.

Exposure to study drug will be summarized using descriptive statistics.

Summaries of AEs will include an overall summary of incidence and summaries by relationship and by severity. Summaries and/or listings will be provided for deaths, SAEs, and AEs leading to discontinuation. Infusion-associated reactions in the ATB200/AT2221 arm will be compared in frequency to the alglucosidase alfa/placebo group in this study. Adverse events will be coded using Medical Dictionary for Regulatory Activities version 18 or higher.

Clinical laboratory results, ECG parameters, and vital signs will be summarized using descriptive statistics (number, mean, median, standard deviation, minimum, and maximum) by treatment group and visit for actual values and changes from baseline. The proportion of subjects with abnormalities will be provided for clinical laboratory results, ECGs, and vital signs. Shift tables will also be provided for clinical laboratory results.

Prior and concomitant medications and nondrug therapies will be summarized by treatment group. Concomitant medications terms will be coded using the World Health Organization Drug Dictionary (September 2013 DDE).

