2. INTRODUCTION

This statistical analysis plan (SAP) describes the planned data derivations, analyses, and statistical methods to be performed for Study ATB200-03. It is based on:

- Protocol for ATB200-03 Amendment 3 dated 14 August 2020
- Amicus standard operating procedure (SOP) ATCRA-SOP-AT-008
- Good Clinical Practices (GCP) and International Conference on Harmonisation (ICH) guidelines E9 (Statistical Principles for Clinical Trials)
- Discussions with Regulatory Authorities

The purpose of this document is to provide details on study populations and on how the variables will be derived, how missing data and intercurrent events will be handled, as well as details on statistical methods to be used to analyze the efficacy and safety data from Study ATB200-03.

The document may evolve over time to reflect protocol amendments, regulatory discussions, and other important changes. However, the final SAP will be finalized, approved by the Sponsor, and placed on file before the database is locked. The data analyses and statistical methods specified in the final SAP supersede those described in the study protocol. Deviations from the final approved plan will be noted in the clinical study report.

Pharmacokinetic (PK) and immunogenicity analyses will be covered in separate analysis plans.

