7.10. Baseline Vital Signs

Baseline vital signs including systolic and diastolic blood pressures (mmHg), heart rate (bpm), and body temperature (°C) will be summarized using descriptive statistics, together with post-baseline data.

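### The SAP's by-visit vital-sign summaries omit respiration rate and temperature, both of which the protocol collects as vital signs; respiration rate is named in no SAP summary

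*SAP*

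**What the plan says.** Protocol 12.3.7 defines the set: "Vital signs include blood pressure (systolic and diastolic), respiration rate, heart rate, and temperature". Protocol 15.3.2.5 then commits to reporting it: "Clinical laboratory results, ECG parameters, and vital signs will be summarized using descriptive statistics", by treatment group and visit, for actual values and changes from baseline. It adds: "The proportion of subjects with abnormalities will be provided for clinical laboratory results, ECGs, and vital signs". Neither sentence restricts which vital signs are meant.

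The SAP is narrower. Section 9.3.1 reads: "Descriptive statistics for vital signs will be presented by treatment group for systolic blood pressure, diastolic blood pressure, heart rate, and body weight". These tables run visit by visit from baseline and include change from baseline. Nothing in the quoted sentence marks the list as examples. Table 10 sets limits of change for pulse rate, systolic and diastolic pressure, and weight. The only listing described in 9.3.1 depends on those limits: "A listing will present all values for a subject and vital sign parameter if at least 1 post-baseline value" meets the criterion for that parameter.

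SAP 7.10, on baseline vital signs, names systolic and diastolic pressure and continues: "heart rate (bpm), and body temperature (°C) will be summarized using descriptive statistics, together with post-baseline data". On precedence, SAP section 2 says: "The data analyses and statistical methods specified in the final SAP supersede those described in the study protocol".

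**The concern.** A programmer who builds the safety tables from 9.3.1 would produce no respiration-rate table, and no other SAP section asks for one. The broader promise in Protocol 15.3.2.5 does not repair this, because the SAP takes precedence. For temperature, 7.10 expects post-baseline data to be shown, while the section that specifies the post-baseline tables does not name it.

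The safety endpoint in both documents includes abnormalities found in the other safety assessments. The protocol describes respiratory failure and diaphragm involvement in late-onset Pompe disease (6.1), and its Table 14 gives tachypnea and fever as signs of a moderate infusion reaction. The two parameters left out of 9.3.1 are therefore ones that the protocol itself treats as relevant. At stake is whether a shift between arms in the scheduled readings would be visible in any planned output.

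**Working it through.** The plan states no figure to reproduce. The check is a comparison of parameter lists, followed by a count of the content affected.

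**Step 1: the lists side by side.**

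| Parameter | Protocol 12.3.7 | SAP 7.10 | SAP 9.3.1 | SAP Table 10 | Protocol Appendix 2 |
|---|---|---|---|---|---|
| Systolic BP | yes | yes | yes | yes | yes |
| Diastolic BP | yes | yes | yes | yes | yes |
| Heart rate | yes | yes | yes | yes (as pulse rate) | yes |
| Temperature | yes | yes | no | no | no |
| Respiration rate | yes | no | no | no | no |
| Body weight | no (measured under 12.3.6) | no | yes | yes | yes |

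Of the 5 parameters in Protocol 12.3.7, 3 are in SAP 9.3.1 and 4 are in SAP 7.10. Respiration rate is in neither.

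**Step 2: is there a fallback listing?** The listing in 9.3.1 needs a Table 10 criterion to trigger it. Table 10 has none for respiration rate or temperature, so neither can appear there. Other safety domains are handled differently. SAP 9.2 ties the laboratory parameters to those in the protocol and lists all results, and SAP 9.3.3 lists all ECG data.

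**Step 3: how much by-visit content is affected?** SAP Table 4 gives the vital-sign windows: Day 1 as the safety baseline, then Weeks 2, 4, 6, 12, 26, 38 and 52. SAP 6.2.7.2 takes one value per window.

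- Values per subject and parameter = 1 + 7 = 8.
- With about 110 planned subjects: 8 × 110 = 880 values per parameter.

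This is a ceiling, before dropout and missed visits.

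**Step 4: compare with the number of readings scheduled.** Protocol Table 10 has vital signs at screening and at every infusion visit.

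- Infusion days from Day 1 to Week 52 = 364/14 + 1 = 27.
- With screening: 27 + 1 = 28 per subject, and 28 × 110 = 3,080 readings per parameter.

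That is 3,080/880 = 3.5 times what a by-visit table could use, so 880 is the relevant figure.

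**The case against.** The strongest reply is that little of clinical importance would be lost, and most of that reply stands.

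- **Table 10.** A reader might infer that Table 10 breaks the protocol's promise of abnormality proportions. It does not. Protocol Appendix 2 has vital-sign criteria for heart rate, systolic and diastolic pressure, and weight only, and Table 10 covers the same four. No parameter with a protocol criterion was dropped.
- **Temperature.** A reader might infer that the SAP both includes and excludes temperature. Section 9.3.1 only fails to name it. Both sections can be followed together, and temperature would then be summarised under 7.10. What remains is that 7.10 does not specify treatment group, visit or change from baseline.
- **Infusion effects.** A reader might infer that acute reactions would go unseen. Protocol 12.2.2 to 12.2.4 place the scheduled assessments before dosing, so these readings were never the means of detecting acute reactions.
- **Other capture.** A reader might infer that respiratory safety goes unreported. Protocol 12.3 requires significant new vital-sign findings that meet the adverse-event definition to be recorded as such. Adverse events and infusion-associated reactions are tabulated by arm, examination findings are summarised by visit, and FVC, SVC, MIP, MEP and SNIP are compared between arms. The disease is a muscle disorder with respiratory involvement, and the plan measures that involvement directly.

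It can also be said that the list in 7.10 opens with a word that leaves it non-exhaustive. That permits a respiration-rate summary but does not plan one. None of these replies supplies the missing by-arm, by-visit table.

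**Conclusion.** The point holds as a minor one. Under the governing SAP, respiration rate has no planned summary and no route into the vital-sign listing. Temperature is missing from the section that specifies the by-arm, by-visit tables. No reason is given for departing from the protocol's commitment, so this looks like an oversight.

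The size is at most 8 by-visit values per subject for each parameter, or 880 across 110 subjects. What could go unseen is a shift in pre-dose respiration rate that is too small to be reported as an adverse event. The documents do not allow an estimate of how likely that is. It would be too strong to say that the data are discarded: they are collected, and only their reporting is unplanned. These are descriptive tables without formal testing, so no estimand, error rate or efficacy conclusion is affected.

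The conclusion assumes that the list in 9.3.1 is read as written and that no separate output specification, outside these documents, adds the two parameters.

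**What to change.** In SAP 9.3.1, add respiration rate and body temperature to the by-visit summaries of actual values and change from baseline by treatment group, keeping weight. In SAP 7.10, add respiration rate. Both sections would then cover every parameter in Protocol 12.3.7.

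New Table 10 rows are not required, since the protocol defines no abnormality limits for these two parameters. In their place, add a sentence to 9.3.1 providing a listing of all values for respiration rate and temperature.

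The cost is a few words in two SAP sections before database lock, two more parameters in an existing table program, and one listing. No new data collection is needed.

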9.3.2. Physical Examination

Complete physical exams are performed at screening and the Week 52 visit. Brief physical exams are performed at Day 1, Weeks 2, 4, 6, 12, 26, and 38. Baseline physical examination results will be presented for each body system/category examined. The number and percentage of subjects judged to be normal, abnormal, or not performed will be summarized.

Further, the results of the physical examinations will be summarized by visit for subjects in the safety population who had an examination post-baseline. Each site/system will be summarized with respect to being normal or abnormal, or not performed.

The supportive data listing will include the information collected on the eCRF (eg, body system/category, result of the observation [eg, normal or abnormal] or not performed, and any investigator comment).

9.3.3. Electrocardiograms

Electrocardiogram data including heart rate [HR] (beats/min), PR interval [PR] (msec), QRS duration (msec), QT interval (msec), QTcB interval (msec), QTcF interval (msec), and R-R interval [RR] (msec) will be summarized at baseline.

The ECG parameters will be summarized by treatment group and visit. Frequency counts will be presented per treatment for both change and absolute values, with changes categorized as per the

bullets below. Individual listings presenting subjects with flags will be created for both change and absolute values. The summary will be tabulated by treatment group.

Additionally, the number and percentage of subjects with the following overall ECG result will be presented:

- Normal
- Abnormal, not clinically significant
- Abnormal, clinically significant

The PDLCs for quantitative ECG data will be summarized by parameter and treatment group. The summary will indicate the number and percentage of subjects with PDLCs at any time during the study and will not be presented by visit. Unscheduled visits will be included in this summary. It is possible for subjects to appear in both categories for any parameters.

The incidence rates will be compared descriptively between treatment groups. There will be no statistical testing.

Table 11 indicates the PDLC criteria for ECG data. All ECG data will be presented in listings.

Table 11: Pre-defined Limits of Change Criteria for ECG Values

ECG Parameter	Criteria
PR interval (msec)	< 120 msec or ≥ 210 msec
QRS duration (msec)	≤ 50 msec or > 120 msec
QTcF interval (msec) and QTcB interval (msec)	Absolute post-baseline QTcB, QTcF, and uncorrected QT interval: ≤ 450 msec or > 450 msec ≤ 480 msec or > 480 msec ≤ 500 msec or > 500 msec
	Change from baseline for QTcB, QTcF, and uncorrected QT: ≤ 30 msec or > 30 msec; ≤ 60 msec or > 60 msec

Abbreviations: bpm = beats per minute; ECG = electrocardiogram; msec = millisecond; PDLC = pre-defined limit of change; QTcB = QT interval for corrected heart rate (based on Bazett’s formula: $QT/(RR^{1/2})$); QTcF = QT interval for corrected heart rate (based on Fridericia’s formula: $QT/(RR^{1/3})$). If the RR is not collected, it will be derived as follows: $RR = (60/HR)$.

9.4. Duration of Therapy and Missing Medication Start and Stop Dates

9.4.1. Missing and Partial Concomitant and Other Medication Start and Stop Dates

Incomplete concomitant medication start dates will be imputed in the same manner as imputation of AE start dates described in Section 9.1.6.1. No imputations will be applied to the medication stop date. If, when using those rules, the stop date is before the start date, then the start date will be left as missing and it will be assumed that the medication is concomitant for the purpose of the analysis. Imputed dates will be flagged in the subject data listings.

9.4.2. Duration of Therapy and Treatment Compliance

Study drug exposure and compliance will be summarized for ATB200 and AT2221 separately. Dose completion (number of administered doses), treatment duration, and treatment compliance will be tabulated. A frequency distribution for the number of treated subjects, and descriptive statistics for the duration of treatment (months) and compliance will be provided by treatment group and for all treated subjects. A summary of treatment duration will also be provided by ERT status.

Duration of treatment (extent of exposure) in months is defined as the number of months on treatment. This will be calculated as: $(\text{date of last dose} - \text{date of first dose} + 1) / 30.4$.

The number and percentages of subjects will be tabulated by the extent of exposure categorized into months as: ≤ 3 , 3 to ≤ 6 , 6 to ≤ 9 , 9 to ≤ 12 , and > 12 .

Note: Due to the potential for delayed visits and catch-up infusions, it is possible that some subjects may stay in the study longer than 12 months.

Compliance for each subject taking ATB200 will be calculated based on the number of infusions as well as the actual infusion dose administered. Compliance based on infusion dose is calculated as:

$$100 * (\text{total infusion dose administered [mg]} / \text{total infusion dose planned or intended [mg]}).$$

Compliance based on number of infusions is calculated as:

$$100 * (\text{number of infusions administered} / \text{number of infusions planned or intended}),$$

where the number of infusions planned is obtained as:

$$(\text{subject's last date in study while on treatment} - \text{date of first infusion} + 14) / 14.$$

Note: Missed infusions due to COVID-19 related policies must be subtracted to ensure accurate compliance.

Compliance for each subject taking AT2221 will be calculated as:

$$100 * (\text{total dose administered [mg]} / \text{scheduled or planned dose [mg]}).$$

Dose compliance rate will be classified as under-compliance: $< 80\%$, within compliance: $(80\%, 120\%)$, and over-compliance: $> 120\%$.

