12. STUDY PARAMETERS AND PROCEDURES

12.1. Schedule of Assessments

The Schedule of Assessments displays each study assessment and procedure along with the scheduled time of occurrence ([Table 10](#)). All study assessments should be conducted by the investigator and/or a suitably qualified designee. Information will be recorded in the source documents and, where appropriate, the eCRF.

If assessments are not able to be completed in 2 days, an additional day may be scheduled. Once established, every effort should be made to maintain the order of procedures, approximately at the same time of day, at each study visit throughout the study, regardless of the number of days that are used for the visit.

Table 10: Schedule of Assessments

Study visit	Screening/Baseline (Day -30 to Day -1) ^a		Treatment						Follow-up
	Screening 1 ^b	Screening 2	Day 1	Infusion visits (every 2 weeks through Week 52) ^c	Weeks 2, 4, 6	Week 12	Week 26, 38	Week 52/ ET ^d	≥ 30 days after last dose
Visit window (days)	—	—	—	± 3	± 3	± 3	± 3	± 3	± 3
Administrative									
Informed consent	X								
Randomization		>Day -10							
Assign subject number	X								
Demographics	X								
Eligibility criteria	X		X						
Schedule next visit	X		X	X	X	X	X	X	
Clinical assessment									
Medical history	X								
Retrospective data collection	See Section 12.3.4.								
Prior/concomitant medications and nondrug therapies	X		X	X	X	X	X	X	X
Complete PE	X							X	
Brief physical examination			X		X	X	X		
Vital signs	X		X	X	X	X	X	X	
Weight ^e	X		X			X	X	X	
Height	X								
AEs/SAEs, including IARs	X	X	X	X	X	X	X	X	X

Table 10: Schedule of Assessments (Continued)

Study visit	Screening/Baseline (Day -30 to Day -1) ^a		Treatment						Follow-up
	Screening 1 ^b	Screening 2	Day 1	Infusion visits (every 2 weeks through Week 52) ^c	Weeks 2, 4, 6	Week 12	Week 26, 38	Week 52/ ET ^d	≥ 30 days after last dose
Visit window (days)	—	—	—	± 3	± 3	± 3	± 3	± 3	± 3
Subject/physician-reported outcomes^f									
R-PAct Scale	X					X	X	X	
PROMIS instruments for physical function, fatigue, dyspnea, upper extremity	X					X	X	X	
EQ-5D-5L	X					X	X	X	
Physician's Global Impression of Change						X	X	X	
Subject's Global Impression of Change						X	X	X	
Laboratory assessments									
12-Lead ECG	X		X			X	X	X	
Serum chemistry, hematology	X		X		X	X	X	X	
Anti-rhGAA Abs (total, cross-reactive, and neutralizing)			X	X ^g	X	X	X	X ^h	X
IgE			X	See Section 12.3.13 .					
Urine pregnancy test (FOCBPs only) ⁱ	X		X	X	X	X	X	X	

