6.1.6. Per-protocol Population

The per-protocol population (PP) is a subset of the mITT population consisting of any mITT subjects who do not have pre-specified protocol deviations that are considered important, as they potentially may have altered the subject's response to study treatment or confounded the study assessments, thereby impacting the analyses of the primary endpoint (6MWD) and the FVC. This population will be analyzed according to the actual treatment received.

The PP population will be characterized separately for sensitivity analyses for the 6MWD and % predicted FVC. The per-protocol population 1 (PP1) will be used for the sensitivity analyses of the 6MWD, while per-protocol population 2 (PP2) will be used for sensitivity analyses of the % predicted FVC.

Pre-specified important protocol deviations leading to exclusion from the PP1 and PP2 populations include those in [Table 2](#). These populations will be determined and finalized before locking the database.

Table 2: Pre-specified Important Protocol Deviations Leading to Exclusion from Per-protocol Populations (PP1 and PP2)

Item	Important Protocol Deviation Description (Excluded from PP1: for 6MWD)	Important Protocol Deviation Description (Excluded from PP2: for FVC)
1.	Subject did not have sufficient treatment exposure (ie, subject did not have at least 80% compliance with study treatment)	Subject did not have sufficient treatment exposure (ie, subject did not have at least 80% compliance with study treatment)
2.	Subject did not have the primary endpoint (6MWD) assessment at the Week 52 visit (including catch-up assessment or delayed visit) due to COVID-19 pandemic or other reasons	Subject did not have FVC assessment at the Week 52 visit (including catch-up assessment or delayed visit) due to COVID-19 pandemic or other reasons
3.	Subject was discontinued from the study for missing at least 5 infusions	Subject was discontinued from the study for missing at least 5 infusions
4.	Subject withdrew consent and/or discontinued from the study	Subject withdrew consent and/or discontinued from the study
5.	Subject was unblinded (accidentally or otherwise) before database lock	Subject was unblinded (accidentally or otherwise) before database lock
6.	Subject was inconsistent in the use/non-use of assisted devices during 6MWT	

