6.2. Derived and Transformed Data

6.2.1. Study Day

The study has no Study Day 0. The date of first dose of study drug (First Dose Date) is labeled as “Day 1” for analysis purposes; it will serve as the reference start date.

Total duration of treatment will be calculated as the difference between the dates of last and first dose of study drug plus 1.

If the date of interest occurs on or after the first dose/randomization date, then study day will be calculated as (date of interest – date of first dose) + 1. If the date of interest occurs prior to the first dose/randomization date, then study day will be calculated as (date of interest – date of first dose).

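### The 12-month exposure cut in SAP 9.4.2 works out at 364.8 days, inside the permitted Week 52 visit window, so the top exposure band mixes on-time completers with extended subjects

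*SAP*

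**What the plan says.** SAP 9.4.2 defines extent of exposure in months as (date of last dose − date of first dose + 1) / 30.4. It then states: "The number and percentages of subjects will be tabulated by the extent of exposure categorized into months as". There are five bands: up to 3 months, above 3 and up to 6, above 6 and up to 9, above 9 and up to 12 (labelled 9 to ≤ 12), and a top band labelled > 12. A note follows directly: "Due to the potential for delayed visits and catch-up infusions, it is possible that some subjects may stay in the study longer than 12 months".

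The planned timing comes from four other places:

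- SAP 6.2.1 makes the first dose date Day 1 and adds: "The study has no Study Day 0".
- SAP 6.2.6.1, Table 3, sets the Week 52 target at Day 365.
- Protocol 12.1, Table 10, has a column headed "Infusion visits (every 2 weeks through Week 52" and gives Week 52 a visit window of ±3 days.
- Protocol 12.3.15.1 times the Week 52 pharmacokinetic samples from just before the infusion to 24 hours after its start.

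On compliance, SAP 9.4.2 opens with "Study drug exposure and compliance will be summarized for ATB200 and AT2221 separately" and continues: "Compliance for each subject taking ATB200 will be calculated based on the number of infusions as well as the actual infusion dose administered". A formula in mg follows for AT2221. Alglucosidase alfa and placebo are not named in these formulas.

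**The concern.** A reader of the exposure table will naturally take the > 12 row as the count of subjects treated beyond the planned year, and the note about delayed visits and catch-up infusions encourages that reading. If the cut lies inside the window allowed for an on-schedule final infusion, the row also contains subjects treated exactly as planned. Which of the two top rows an on-time completer enters then depends on a day or two of scheduling. The table would overstate the number with extended exposure and could not be used to find the subjects whose treatment was prolonged by COVID-19 disruption.

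**Working it through.** **Inputs**

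- Divisor 30.4 and band limit 12 months (SAP 9.4.2)
- First dose = Day 1 (SAP 6.2.1)
- Week 52 target day = 365 (SAP 6.2.6.1, Table 3)
- Visit window ±3 days (Protocol 12.1, Table 10)
- Catch-up example ending with an infusion at Week 54 (SAP 4.5.1)

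**Step 1. Reproduce the plan's own figure.** Week 52 target = 52 × 7 + 1 = 365, which agrees with Table 3. The same rule gives 85, 183 and 267 for Weeks 12, 26 and 38, also as tabulated.

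**Step 2. Convert the cut to days.** 12 × 30.4 = 364.8 days. The permitted window is 365 − 3 = Day 362 to 365 + 3 = Day 368, so the cut lies inside it. Because first dose is Day 1, the numerator of the formula equals the study day of the last dose.

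**Step 3. Apply the formula to each permitted day, unrounded.**

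| Day of last dose | Day / 30.4 | Band |
|---|---|---|
| 362 | 11.91 | 9 to ≤ 12 |
| 363 | 11.94 | 9 to ≤ 12 |
| 364 | 11.97 | 9 to ≤ 12 |
| 365 (target) | 12.01 | > 12 |
| 366 | 12.04 | > 12 |
| 367 | 12.07 | > 12 |
| 368 | 12.11 | > 12 |

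Four of the seven permitted days fall in the top band, including the target day. At the target the excess is only 365 − 364.8 = 0.2 day.

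**Step 4. Compare with an extended subject.** In the catch-up example of SAP 4.5.1 the final infusion is at Week 54: 54 × 7 + 1 = Day 379, and 379 / 30.4 = 12.47 months. This subject shares a band with the on-time completers of Days 365 to 368.

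**Step 5. Try a more exact month.** With 365.25 / 12 = 30.4375 days, the cut is 365.25 days. Day 365 becomes 11.99 and moves down, but Days 366 to 368 still give 12.02 to 12.09. Changing the divisor alone does not take the cut out of the window.

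**Step 6. Test the last-dose assumption.** If dosing ended at Week 50 (50 × 7 + 1 = Day 351), the value would be 351 / 30.4 = 11.55 and on-time completers would all be in 9 to ≤ 12. The infusion column through Week 52, and the Week 52 samples timed around an infusion, point to Week 52 as the last dose.

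**The case against.** **The band has no stated purpose.** The SAP does not reserve the > 12 band for delayed subjects. The bands are neutral, and the note says only that longer stays can occur. This stands: calling on-time completers misclassified would assume a definition that the SAP never gives. What remains is that the band does not separate the two groups.

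**Rounding.** The result depends on unrounded values. At one decimal, Days 365 and 366 both become 12.0 and drop to the lower band, leaving two of seven days above 12. SAP 9.4.2 states no rounding rule. Elsewhere the SAP writes rounding into a formula when it wants it (FLOOR for age in 6.2.3, ROUND for ERT duration in 7.4), so unrounded is the plainer reading. Either way the cut splits the window.

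**Last dose.** The catch-up example in SAP 4.5.1 puts end-of-study assessments after the last make-up infusion and mentions no dose on the assessment day. That leaves some doubt about a Week 52 infusion, though the protocol's schedule favours one.

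**Other outputs.** SAP 9.4.2 also summarises duration as a continuous variable and the number of doses. COVID-19 misses are recorded as deviations (SAP 4.5.1), and all deviations are listed (SAP 7.3). A reader might infer that the table hides the extended subjects; these other outputs would still show them.

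**Compliance.** A reader might also infer that the 80% exclusion in SAP Table 2 ("subject did not have at least 80% compliance with study treatment") can be applied only to the test arm, making the per-protocol analyses asymmetric. The documents do not support this. SAP 9.4.2 promises compliance by treatment group, SAP 4.2 counts both regimens as study drug, and Table 2 has no arm restriction. The infusion formulas carry over unchanged to alglucosidase alfa; placebo needs only a capsule count.

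**Conclusion.** The point holds as a minor defect in a descriptive table. As written, the 12-month cut is 364.8 days and lies within the window for an on-schedule final infusion, so the top band combines planned with extended exposure. This rests on two assumptions: that the Week 52 infusion is the last dose, and that months are not rounded before banding.

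The number of subjects affected cannot be obtained from the documents. Four of seven days (4 / 7 = 57%) would be a share of on-time completers only if last doses were spread evenly over the window, which nothing in the documents supports; it is illustrative only. A claim that most on-time completers will be shown as over-treated goes too far.

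The primary MMRM on ITT-OBS, the key secondary ANCOVA on ITT-LOCF and the per-protocol analyses are unaffected. The absence of the control products from the compliance formulas is a matter of wording, not an error.

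**What to change.** Band on the day count and start the top band above the Week 52 visit window, at more than 368 days. The lower limits can stay where they are: 3, 6 and 9 months of 30.4 days are 91.2, 182.4 and 273.6 days. The bands become ≤ 91, 92 to 182, 183 to 273, 274 to 368 and > 368 days. The catch-up example (Day 379) then falls in the top band and every in-window completer falls below it.

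The exact limit is a choice. Protocol 13.3.3 treats a dose as missed only when it cannot be scheduled within 7 days, so a limit of 365 + 7 = 372 days could also be defended. It too lies below Day 379. A footnote should state the rule chosen.

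Optionally, align the compliance wording with SAP 9.1.5, which already pairs ATB200 with alglucosidase alfa and AT2221 with placebo, and use capsule counts for the capsules.

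The cost is a short SAP edit and a small programming change. No data collection or efficacy analysis is touched.
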